## 12.3 Patient Information and Informed Consent

After the study has been fully explained, written informed consent will be obtained from either the patient or his/her guardian or legal representative before study participation. The method of obtaining and documenting the informed consent and the contents of the consent must comply with the ICH-GCP and all applicable regulatory requirements.

The City of Hope Data Coordinating Center will provide the Site Investigator with a sample consent form. Local and/or institutional requirements may require disclosure of additional information in the informed consent. Any changes to the consent form must be submitted to the COH DCC for approval, prior to submission to the IRB/IEC. The IRB/IEC will review the consent form for approval. A copy of the approved form must be submitted to the COH DCC prior to initiation of the study.

Before implementing any study procedure, informed consent shall be documented by the use of a written consent form approved by the IRB/IEC and signed and dated by the patient or the patient's legally authorized representative at the time of consent. A copy of the signed informed consent will be given to the patient or patient's legally authorized representative. The original signed consent must be maintained by the Site Investigator and available for inspection by the COH DCC, its designated representatives, or regulatory authority at any time.

#### **12.4 Patient Confidentiality**

In order to maintain patient privacy, all data capture records, drug accountability records, study reports and communications will identify the patient by initials and the assigned patient number. If requested, the investigator will grant monitor(s) and auditor(s) from City of Hope, Millennium/Celgene or its designees and regulatory authority (ies) access to the patient's original medical records for verification of data gathered on the data capture records and to audit the data collection process. The patient's confidentiality will be maintained and will not be made publicly available to the extent permitted by the applicable laws and regulations.

The investigator/institution will permit direct access to source data and documents by the COH DCC staff, its designees, the FDA, and other applicable regulatory authorities. The access may consist of trial-related monitoring, including remote monitoring, audits, IRB/IEC reviews, and FDA/regulatory authority inspections.

Release of research results should preserve the privacy of medical information and must be carried out in accordance with Department of Health and Human Services Standards for Privacy of Individually Identifiable Health Information, 45 CFR 164.508.

#### **12.5 Investigator Compliance**

The investigator will conduct the study in compliance with the protocol given approval/favorable opinion by the IRB and the appropriate regulatory authority(ies). Changes to the protocol will require approval from Millennium/Celgene and written IRB approval/favorable opinion from City of Hope (as the sponsor) prior to implementation, except when the

modification is needed to eliminate an immediate hazard(s) to patients. The IRB may provide, if applicable regulatory authority(ies) permit, expedited review and approval/favorable opinion for minor change(s) in ongoing studies that have the approval /favorable opinion of the IRB. The investigator will submit all protocol modifications to Millennium/Celgene and the regulatory authority(ies) in accordance with the governing regulations.

Any departures from the protocol must be fully documented in the source documents.

## **12.6 Study Documentation and Archives**

### **12.6.1 Source Documents**

Source documents are original documents, data, and records (e.g., medical records, data collection forms, pharmacy dispensing records, recorded data from automated instruments, laboratory data) that are relevant to the clinical trial. The Site Investigator or their designee will prepare and maintain adequate and accurate source documents. These documents are designed to record all observations and other pertinent data for each patient enrolled in this clinical trial. Source documents must be adequate to reconstruct all data transcribed onto the case report forms.

### **12.6.2 Case Report Form Completion**

All data will be collecting using COH data collection forms via an electronic data capture system, Medidata RAVE. All case report forms must be completed by designated study personnel. The completed case report forms must be reviewed, signed and dated by the Site Investigator or designee in a timely fashion.

#### **All data will be submitted as follows:**

- **Eligibility Checklist:** the participating institutions at the registering site will have completed and faxed this form at the time of registration.
- **On-Study/Baseline Forms:** completed on-study forms are due within two weeks of registration.
- **Treatment Forms (Cycle Forms):** completed forms are due within 2 weeks of completion of a cycle (unless needed sooner for DLT assessment during Phase I). The City of Hope Data Coordinating center will communicate with site staff if forms are needed sooner.

- **Adverse Event Collection:** completed adverse events are due within two weeks of a cycle (unless needed sooner for DLT assessment during Phase I). The City of Hope Data Coordinating center will communicate with site staff if forms are needed sooner.
- **Response/Off Treatment/Off Study/Follow-Up:** forms will be completed each time a patient is evaluated for response, comes off treatment, new follow-up information is obtained or comes off study.

## 12.7 Archival of Records

According to 21 CFR 312.62I, the Site Investigators shall retain records required to be maintained under this part for a period of 2 years following the date a marketing application is approved for the drug for the indication for which it is being investigated. If no application is to be filed or if the application is not approved for such indication, the Site Investigator shall retain these records until 2 years after the investigation is discontinued and the FDA or applicable regulatory authorities are notified.

The Site Investigator must retain protocols, amendments, IRB/IEC approvals, copies of the Form FDA1572, signed and dated consent forms, medical records, case report forms, drug accountability records, all correspondence, and any other documents pertaining to the conduct of the study.

## 12.8 Study Monitoring and Data Collection

Following initiation of the study site, remote monitoring will be completed by the COH DCC. The Site Investigator will allocate sufficient time for the designated site staff to submit source documentation as required to complete remote monitoring.

The purpose of trial monitoring is to verify the following:

- The rights and well-being of human subjects are protected.
- The reported data are accurate, complete, and verifiable from source documents.
- The conduct of the trial is in compliance with the currently approved protocol, amendment(s), ICH GCP, FDA CFR, and any other applicable regulatory requirements.

The COH DCC will submit a prepare a written report after each remote monitoring timepoint or trial related communication. Reports shall include a summary of what the monitor reviewed

remotely and significant findings, deviations and deficiencies, conclusions, actions taken or to be taken to ensure site compliance.

City of Hope's Data Coordinating Center, regulatory authorities, the IRB and/or Millennium/Celgene may request access to all source documents, data capture records, and other study documentation for on-site audit, inspection and remote monitoring. Direct access to these documents must be guaranteed by the investigator, who must provide support at all times for these activities.

## **12.9      Investigator and Site Responsibility for Drug Accountability**

Accountability for the study drug at all study sites is the responsibility of the principal investigator. The investigator will ensure that the drug is used only in accordance with this protocol. Drug accountability records for each respective drug/company, MLN9708 for Millennium and pomalidomide for Celgene indicating the drug's delivery date to the site, inventory at the site, use by each patient, and amount returned to Millennium/Celgene or a designee or disposal of the drug (if applicable and if approved by Millennium/Celgene) will be maintained by the clinical site. Accountability records will include dates, quantities, lot numbers, expiration dates (if applicable), and patient numbers. Accountability records will need to be submitted to the COH DCC as requested.

## **12.10     MLN9708 Product Complaints**

A product complaint is a verbal, written, or electronic expression that implies dissatisfaction regarding the identity, strength, purity, quality, or stability of a drug product. Individuals who identify a potential product complaint situation should immediately contact MedComm Solutions (see below) and report the event. Whenever possible, the associated product should be maintained in accordance with the label instructions pending further guidance from a Millennium Quality representative.

For Product Complaints, call MedComm Solutions at [contact] ([name]) (US and International)

--

Product complaints in and of themselves are not AEs. If a product complaint results in an SAE, an SAE form should be completed and sent to Millennium.

## **12.11 Closure of the Study**

This study may be prematurely terminated, if in the opinion of the investigator or Millennium/Celgene, there is sufficient reasonable cause. Written notification documenting the reason for study termination will be provided to the investigator or Millennium/Celgene by the terminating party.

Circumstances that may warrant termination include, but are not limited to:

- Determination of unexpected, significant, or unacceptable risk to patients
- Failure to enter patients at an acceptable rate
- Insufficient adherence to protocol requirements
- Insufficient, incomplete and/or unevaluable data
- Determination of efficacy based on interim analysis
- Plans to modify, suspend or discontinue the development of the drug

## **12.12 Record Retention**

The investigator will maintain all study records according to the ICH-GCP and applicable regulatory requirement(s).

## **13. USE OF INFORMATION**

All information regarding MLN9708 supplied by Millennium and pomalidomide by Celgene to the investigator is privileged and confidential information. The investigator agrees to use this information to accomplish the study and will not use it for other purposes without consent from Millennium/Celgene. It is understood that there is an obligation to provide Millennium/Celgene with complete data obtained during the study. The information obtained from the clinical study will be used toward the development of MLN9708 and may be disclosed to regulatory authority(ies), other investigators, corporate partners, or consultants as required.

Upon completion of the clinical study and evaluation of results by Millennium/Celgene, the hospital or institution and/or investigator may publish or disclose the clinical trial results pursuant to the terms contained in the applicable Clinical Trial Agreement.

## 15. APPENDICES

### 15.1 Eastern Cooperative Oncology Group (ECOG) Scale for Performance Status

Grade	Description
0	Normal activity. Fully active, able to carry on all predisease performance without restriction
1	Symptoms but ambulatory. Restricted in physically strenuous activity, but ambulatory and able to carry out work of a light or sedentary nature (eg, light housework, office work)
2	In bed < 50% of the time. Ambulatory and capable of all self-care, but unable to carry out any work activities. Up and about more than 50% of waking hours.
3	In bed > 50% of the time. Capable of only limited self-care, confined to bed or chair more than 50% of waking hours.
4	100% bedridden. Completely disabled. Cannot carry on any self-care. Totally confined to bed or chair
5	Dead

Source: Oken MM, Creech RH, Tormey DC, Horton J, Davis TE, McFadden ET et al. Toxicity and response criteria of the Eastern Cooperative Oncology Group. Am J Clin Oncol 1982; 5 (6):649-55.

## 15.2 Cockcroft-Gault Equation

For males:

$$\text{Creatinine Clearance} = \frac{(140 - \text{age}[years] \times \text{weight [kg]})}{72 \times (\text{serum creatinine[mg/dL]})} \quad \text{OR} \quad \frac{(140 - \text{age}[years] \times \text{weight [kg]})}{0.81 \times (\text{serum creatinine}[\mu\text{mol/L}])}$$

For females:

$$\text{Creatinine Clearance} = \frac{0.85 (140 - \text{age}[years] \times \text{weight [kg]})}{72 \times (\text{serum creatinine[mg/dL]})} \quad \text{OR} \quad \frac{0.85 (140 - \text{age}[years] \times \text{weight [kg]})}{0.81 \times (\text{serum creatinine}[\mu\text{mol/L}])}$$

Source: Cockcroft DW, Gault MH. Prediction of creatinine clearance from serum creatinine. Nephron 1976;16(1):31-41.

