- 4) All patients must be counseled about pregnancy precautions, risks of fetal exposure and other risks. All patients enrolled into this trial, must be registered in and must comply with all requirements of the POMALYST REMS™ program.
- 5) CBC to be performed and reviewed by clinician within 24 hours of day of dosing (first day of each cycle). Alternately, a STAT CBC may be drawn on day of dosing, however should be reviewed prior to administration of investigational product(s). Serum Chemistry to be performed and reviewed by the investigator within 24 hours of day of dosing (first day of each cycle). Alternately, a STAT CMP may be drawn on day of dosing however should be reviewed by the investigator prior to administration of investigational product(s). Chemistry includes: glucose, calcium, albumin, total protein, sodium, potassium, BUN, creatinine, ALP, ALT, AST, bilirubin and uric acid (uric acid to be drawn at screening and then as needed based on tumor lysis syndrome risk). Weight and serum creatinine will be used to calculate creatinine clearance by Cockcroft-Gault equation (see appendix 15.2).
- 6) Neurological assessment required at screening and Day 1 of Cycle 2+.
- 7) Extramedullary Disease: prior to study (28 days), testing required only if extramedullary disease is present, every 12 weeks (if present at screening) or upon clinical suspicion of progressive disease (if present at screening). This may include CT scan of the abdomen/pelvis, CT or x-ray of the chest, ultrasound of the liver/spleen or abdomen.
- 8) Skeletal survey (including skull, all long bones, pelvis and chest) with tumor measurements (measurements required if plasmacytomas are present). Also required if previous survey >28 days from study entry and at any time when clinically indicated.
- 9) A bone marrow aspiration and biopsy is required at screening; Repeat bone marrow biopsy/aspirate as appropriate to confirm achievement of response (aspirate only—biopsy not required).
- 10) Myeloma lab tests: B2Microglobulin (collected at screening only); serum immunoelectrophoresis, immunoglobulin assay, M band quantitation by immunofixation, free light chain and 24 hour urine collection for Bence Jones protein to be performed at baseline prior to study, prior to each cycle (to confirm complete response and in patients with urine only measurable disease) thereafter and at time of end of treatment (if last tests were > 3 weeks).

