  - Platelet count  $\geq 75,000/\mu\text{L}$  for patients in whom  $< 50\%$  of bone marrow nucleated cells are plasma cells; or a platelet count  $\geq 50,000/\mu\text{L}$  for patients in whom  $\geq 50\%$  of bone marrow nucleated cells are plasma cells. Platelet transfusions are not allowed within 3 days of last platelet assessment to confirm eligibility.
  - Total bilirubin  $\leq 1.5 \times$  the institutional upper limit of the normal range (IULN).
  - Alanine aminotransferase (ALT) and aspartate aminotransferase (AST)  $\leq 3 \times$  IULN.
  - Calculated creatinine clearance  $\geq 45\text{mL/min}$  (see Appendix 15.2).

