#### **10.1.2 Populations for Analysis**

**Phase I (Evaluable for Toxicity):** Patients will be considered evaluable for toxicity if they receive any study drug. Patients will be considered evaluable for dose limiting toxicity if they receive at least 75% of both Pomalidomide and MLN9708 and are followed for the full 28 days during cycle 1 or experience a DLT. All patients who are not evaluable for dose limiting toxicity will be replaced.

**Phase II (Evaluable for Toxicity):** Patients will be considered evaluable for toxicity if they receive any study drug. Patients in Phase II will not be replaced based on toxicity.

**Phase I and II (Evaluable for Response):** For the phase II portion, as part of the primary analysis, patients will be considered evaluable for response if they are eligible, have baseline disease assessments, and receive any protocol treatment. As part of a secondary analysis, patients will be considered evaluable for response if they have baseline disease assessments, receive at least 75% of both Pomalidomide and MLN9708 during the first cycle of therapy and have had their disease re-evaluated. Patients will have their response classified according to the IMWG response criteria. All patients in phase II and those treated at the RP2D in phase I, who are not evaluable for response will be replaced.

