## 15.2 Cockcroft-Gault Equation

For males:

$$\text{Creatinine Clearance} = \frac{(140-\text{age}[years] \times \text{weight [kg]})}{72 \times (\text{serum creatinine[mg/dL]})} \quad \text{OR} \quad \frac{(140-\text{age}[years] \times \text{weight [kg]})}{0.81 \times (\text{serum creatinine}[\mu\text{mol/L}])}$$

For females:

$$\text{Creatinine Clearance} = \frac{0.85 (140-\text{age}[years] \times \text{weight [kg]})}{72 \times (\text{serum creatinine[mg/dL]})} \quad \text{OR} \quad \frac{0.85 (140-\text{age}[years] \times \text{weight [kg]})}{0.81 \times (\text{serum creatinine}[\mu\text{mol/L}])}$$

Source: Cockcroft DW, Gault MH. Prediction of creatinine clearance from serum creatinine. Nephron 1976;16(1):31-41.

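### Appendix 15.2 closes the bracket of the creatinine clearance formula after weight instead of after age, so the formula as printed gives a negative value for every realistic adult and cannot be used to test the 45 mL/min entry criterion.

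*Combined protocol and SAP*

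**What the plan says.** Appendix 15.2 (Cockcroft-Gault Equation) gives four expressions. The male numerator is "140 - \text{age}[years] \times \text{weight [kg", with one bracket opening before 140 and closing after weight. The female numerator is "0.85 (140 - \text{age}[years] \times \text{weight [kg", bracketed in the same way. The denominators are "72 \times (\text{serum creatinine[mg/dL" and "0.81 \times (\text{serum creatinine}[\mu\text{mol/L" for the two creatinine units. The combined file contains the protocol text twice, and the second Appendix 15.2 prints the same numerator: "140-\text{age}[years] \times \text{weight [kg".

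Two operative places send sites to this appendix:

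- Section 5.1, criterion 9, and the matching item in the Protocol Summary: "Calculated creatinine clearance" must be at least 45 mL/min, with a reference to Appendix 15.2.
- Schedule of Events, footnote 5: "Weight and serum creatinine will be used to calculate creatinine clearance by Cockcroft-Gault equation (see appendix 15.2").

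The appendix names the equation in its heading and cites the source paper. No other section prints the formula in a different form.

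**The concern.** By ordinary precedence the printed numerator is 140 minus the product of age and weight. For any adult that product is in the hundreds or thousands, so the clearance is negative. A negative clearance has no physical meaning, and it can never meet a floor of 45 mL/min.

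At stake is the written rule behind an entry criterion that is verified. Section 6 has the coordinating center check eligibility before it accepts a registration, and Appendix 15.5 has it checked again during monitoring. Anyone who calculates from the appendix as printed gets an unusable number.

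**Working it through.** **Inputs.** The formula and the constants 140, 72, 0.81 and 0.85 come from Appendix 15.2. The 45 mL/min floor and the minimum age of 18 come from Section 5.1. The documents give no worked clearance value to reproduce and no example patient, so every age, weight and creatinine below is an assumption.

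**Formulas (mg/dL, male; multiply by 0.85 for females).**

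- As printed: (140 − age × weight) / (72 × creatinine)
- Bracket closed after age: (140 − age) × weight / (72 × creatinine)

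**When the printed form is negative.** Whenever age × weight > 140. At 18 years that is a weight above 140/18 = 7.8 kg; at 65 years, above 140/65 = 2.2 kg.

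**Whether it could ever reach 45.** Even if age × weight were zero, the printed male form could not exceed 140/(72 × creatinine), which is 1.9 mL/min at 1.0 mg/dL.

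**Example patients (mL/min).**

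| Assumed patient | As printed | Bracket after age |
|---|---|---|
| Male, 65 y, 70 kg, 1.0 mg/dL | (140 − 4550)/72 = −61 | 75 × 70/72 = 73 |
| Female, 65 y, 70 kg, 1.0 mg/dL | 0.85 × (140 − 4550)/72 = −52 | 0.85 × 75 × 70/72 = 62 |
| Male, 80 y, 55 kg, 1.1 mg/dL | (140 − 4400)/79.2 = −54 | 60 × 55/79.2 = 42 |
| Male, 50 y, 90 kg, 0.9 mg/dL | (140 − 4500)/64.8 = −67 | 90 × 90/64.8 = 125 |

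With the bracket moved, 45 mL/min separates these patients in a sensible way: three qualify and one does not. As printed, none qualifies.

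**µmol/L form.** Assuming 88.4 µmol/L per mg/dL, the female patient above gets −52.4 as printed and 62.3 with the bracket moved. The problem is the same in both units.

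**Range.** Over 63,336 assumed combinations for the male mg/dL form (18 to 95 years, 35 to 150 kg, creatinine 0.4 to 3.0 mg/dL), the highest printed-formula value was −2.3 mL/min, at 18 years, 35 kg and 3.0 mg/dL. None reached 45.

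**Ordering.** The printed form also reverses the role of creatinine. For the 65-year-old man of 70 kg, raising creatinine from 1.0 to 3.0 mg/dL moves the result from −61 up to (140 − 4550)/216 = −20, so worse renal function gives a higher value.

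**Where the bracket belongs.** Three points within the documents favour closing it after age. In the male forms a bracket around the whole numerator of a fraction does nothing. Subtracting age from 140 subtracts years from a plain constant, whereas the printed form subtracts a product of years and kilograms. And only the moved bracket gives values on the scale of the 45 mL/min floor.

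**The case against.** There are four fair objections.

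First, the equation was typeset and then read from PDF by a program, and the point rests on the position of one closing bracket. All eight numerators across the two copies place it the same way, which favours a real misprint. But the copies repeat one page and the forms share one layout, so a systematic misreading could repeat too. This stands as a caveat: the original page must be checked.

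Second, a reader might infer that no patient could be enrolled. The documents do not support that. The heading of Appendix 15.2 names the equation, the source is cited, and footnote 5 asks for clearance by that named equation. A site would probably use a standard calculator, and an impossible value would be noticed with the first patient.

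Third, a reader might infer that an automated check built from the appendix would reject everyone. No section describes such a check. Under Section 6, sites email the eligibility checklist and source documents, and coordinating center staff verify them before accepting registration. Appendix 15.5 places electronic data capture after registration.

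Fourth, a reader might infer harm to the primary analysis, because Section 10.1.2 says that "patients will be considered evaluable for response if they are eligible, have baseline disease assessments, and receive any protocol treatment". The link exists on paper, but an error that gives an absurd value for every patient does not quietly misclassify some of them. No route to a changed denominator or estimate can be shown.

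The last three objections limit the consequences. They do not make the printed formula correct.

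**Conclusion.** The formula is wrong as printed, and this can be seen from the documents alone: an entry floor of 45 mL/min is tied to an expression that is negative for every realistic adult. The finding rests on ordinary operator precedence, on the extracted text matching the original page, and on assumed patient values, although the sign condition (age × weight above 140) needs no particular patient.

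The corrected form is strongly suggested by the printed constants and by the plausible values it yields, but it should be confirmed against the cited source, which was not available here.

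This is a minor correction to an eligibility formula. It does not affect the design, the sample size or any planned estimate, and the 45 mL/min threshold itself is not questioned.

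**What to change.** Check Appendix 15.2 on the original page and against the source it cites. If the bracket is as printed here, replace the numerator by (140 − age[years]) × weight[kg], with the factor 0.85 for females, in all four forms and in both copies of the appendix. Confirm that any calculation used with the eligibility checklist has the same expression.

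The cost is one moved bracket per form. No threshold, population or analysis changes, and there is no statistical downside.
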